8.2 Follow-up Visits

Follow-up visits are scheduled in reference to study vaccination dates as indicated for each visit window.

**8.2.1 Visit 02, Day 2, Clinic Visit, All Treatment Arms
(Window: Day 2+1 day post first study vaccination)**

- Interim medical history, including an assessment for new medical conditions, stability of chronic diseases and symptoms suggestive of PIMMCs, will be obtained by interview of subjects and any changes since the previous clinic visit or phone call will be noted.
- All concomitant medications (including solicitation for receipt of any non-study influenza vaccines) will be recorded on the appropriate DCF.
- All AE/SAEs will be recorded on the appropriate DCF.
- Memory Aid information will be reviewed with subjects.
- A targeted physical examination, including an assessment for signs suggestive of PIMMCs, may be performed, if indicated based on review of interim medical history, by a study clinician licensed to make medical diagnoses and listed on the Form FDA 1572 as the site PI or sub-investigator.
- The first study vaccination site will be examined.
- Approximately 4 mL of venous blood will be collected for cellular immunology assays.
- Approximately 16 mL of venous blood will be collected for future research.

**8.2.2 Visit 03, Day 4, Clinic Visit, All Treatment Arms
(Window: Day 4+1 day post first study vaccination)**

- Interim medical history, including an assessment for new medical conditions, stability of chronic diseases and symptoms suggestive of PIMMCs, will be obtained by interview of subjects and any changes since the previous clinic visit or phone call will be noted.
- All concomitant medications (including solicitation for receipt of any non-study influenza vaccines) will be recorded on the appropriate DCF.
- All AE/SAEs will be recorded on the appropriate DCF.
- Memory Aid information will be reviewed with subjects.
- A targeted physical examination, including an assessment for signs suggestive of PIMMCs, may be performed, if indicated based on review of interim medical history, by

a study clinician licensed to make medical diagnoses and listed on the Form FDA 1572 as the site PI or sub-investigator.

- The first study vaccination site will be examined.
- Approximately 8 mL of venous blood will be collected for cellular immunology assays.
- Approximately 16 mL of venous blood will be collected for future research.

8.2.3 Visit 04, Day 8, Clinic Visit, All Treatment Arms (Window: Day 8-1/+2 days post first study vaccination)

- Interim medical history, including an assessment for new medical conditions, stability of chronic diseases and symptoms suggestive of PIMMCs, will be obtained by interview of subjects and any changes since the previous clinic visit or phone call will be noted.
- All concomitant medications (including solicitation for receipt of any non-study influenza vaccines) will be recorded on the appropriate DCF.
- All AE/SAEs will be recorded on the appropriate DCF.
- Memory Aid information will be reviewed with subjects.
- A targeted physical examination, including an assessment for signs suggestive of PIMMCs, may be performed, if indicated based on review of interim medical history, by a study clinician licensed to make medical diagnoses and listed on the Form FDA 1572 as the site PI or sub-investigator.
- The first study vaccination site will be examined.
- Approximately 10 mL of venous blood will be collected for clinical safety labs (WBC, Hgb, PLT, ALT, T. Bili, Cr) to be performed by the central (clinical) laboratory.
- Approximately 44 mL of venous blood will be collected for cellular immunology assays.
- Approximately 21 mL of venous blood will be collected for future research.

Note: Subjects that complete this visit on Day 7 will be reminded to complete their Memory Aid through the end of Day 8, and study personnel will contact these subjects by phone to review their Memory Aid information and solicit any AE/SAEs and concomitant medications (including solicitation for receipt of any non-study influenza vaccines). Based on the information collected, subjects may be asked to return to the clinic for evaluation.

8.2.4 Visit 05, Day 15, Clinic Visit, All Treatment Arms (Window: Day 15±1 day post first study vaccination)

- Interim medical history, including an assessment for new medical conditions, stability of chronic diseases and symptoms suggestive of PIMMCs, will be obtained by interview of subjects and any changes since the previous clinic visit or phone call will be noted.
- All concomitant medications (including solicitation for receipt of any non-study influenza vaccines) will be recorded on the appropriate DCF.
- All AE/SAEs will be recorded on the appropriate DCF.
- A targeted physical examination, including an assessment for signs suggestive of PIMMCs, may be performed, if indicated based on review of interim medical history, by a study clinician licensed to make medical diagnoses and listed on the Form FDA 1572 as the site PI or sub-investigator.
- Approximately 8 mL of venous blood will be collected for cellular immunology assays.
- Approximately 16 mL of venous blood will be collected for future research.

8.2.5 Clinic Visit, Treatment Arms 2, 3, 5, and 6

Visit 06, Day 22 (Window: Day 22+7 days post first study vaccination), Treatment Arms 2, 3, 5, and 6

- Interim medical history, including an assessment for new medical conditions, stability of chronic diseases and symptoms suggestive of PIMMCs, will be obtained by interview of subjects and any changes since the previous clinic visit or phone call will be noted.
- All concomitant medications (including solicitation for receipt of any non-study influenza vaccines) will be recorded on the appropriate DCF.
- All AE/SAEs will be recorded on the appropriate DCF.
- A targeted physical examination, including an assessment for signs suggestive of PIMMCs, may be performed, if indicated based on review of interim medical history, by a study clinician licensed to make medical diagnoses and listed on the Form FDA 1572 as the site PI or sub-investigator.
- Approximately 15 mL of venous blood will be collected for serological assays.

- Approximately 16 mL of venous blood will be collected for future research.

8.2.6 Safety Follow-up, Phone Call, Treatment Arms 2, 3, 5, and 6

Visit 07, Day 61 (Window: Day 61±7 days post first study vaccination), Treatment Arms 2, 3, 5, and 6

Subjects will be contacted by phone to query for safety events and concomitant medications (including solicitation for receipt of any non-study influenza vaccines). AEs limited to SAEs and MAAEs, including NOCMCs and PIMMCs, that have occurred since the previous clinic visit or phone call will be solicited. Based on the information collected, subjects may be asked to return to the clinic for evaluation.

8.2.7 Second Study Vaccination (Dose 2), Clinic Visit, All Treatment Arms

Visit 06, Day 22 (Window: Day 22+7 days post first study vaccination), Treatment Arms 1 and 4

Visit 08, Day 121 (Window: Day 121-7/+14 days post first study vaccination), Treatment Arms 2, 3, 5, and 6

- Eligibility criteria will be reviewed with subjects prior to the second study vaccination to ensure continued eligibility.
- For a subject to receive the second study vaccination, refer to [Section 5.2.3](#) for additional second study vaccination eligibility criteria.
- Interim medical history, including an assessment for new medical conditions, stability of chronic diseases and symptoms suggestive of PIMMCs, will be obtained by interview of subjects prior to the second study vaccination. Any changes in medical history since the first study vaccination will be reviewed with subjects prior to the second study vaccination to ensure continued eligibility.
- All concomitant medications (including solicitation for receipt of any non-study influenza vaccines) will be recorded on the appropriate DCF prior to the second study vaccination. Any new concomitant medications taken since the first study vaccination will be reviewed with subjects prior to the second study vaccination to ensure continued eligibility.
- All AE/SAEs will be recorded on the appropriate DCF prior to the second study vaccination. Note: AEs will be limited to SAEs and MAAEs, including NOCMCs and

PIMMCs, for subjects who are discontinued from receipt of the second study vaccination and being followed for safety.

- Vital signs, including oral temperature, pulse and BP, will be obtained prior to the second study vaccination to ensure continued eligibility. Subjects must not eat or drink anything hot or cold, or smoke within 10 minutes prior to taking oral temperature. Note: Vital signs are not required for subjects who are discontinued from receipt of the second study vaccination and being followed for safety.
- A targeted physical examination, including an assessment for signs suggestive of PIMMCs, may be performed prior to the second study vaccination, if indicated based on review of interim medical history, by a study clinician licensed to make medical diagnoses and listed on the Form FDA 1572 as the site PI or sub-investigator.
- A urine or serum pregnancy test will be performed locally by the site within 24 hours prior to the second study vaccination for all women of childbearing potential. Results must be negative and known prior to the second study vaccination.
- Approximately 10 mL of venous blood will be collected immediately prior to the second study vaccination for clinical safety labs (WBC, Hgb, PLT, ALT, T. Bili, Cr) to be performed by the central (clinical) laboratory. The results from these evaluations will not be available or reviewed prior to the second study vaccination.
- Approximately 15 mL of venous blood will be collected immediately prior to the second study vaccination for serological assays.
- Approximately 32 mL of venous blood will be collected immediately prior to the second study vaccination for cellular immunology assays.
- Approximately 16 mL of venous blood will be collected immediately prior to the second study vaccination for future research.
- Pre-administration reactogenicity assessments will be performed immediately prior to the second study vaccination to establish baseline.
- Subjects will then receive one- 0.5 mL dose of study vaccine via a single IM injection into the deltoid muscle of the subjects' preferred arm. The second study vaccination may be given in the same preferred arm as long as there is no interference with the reactogenicity assessment. The site of injection (right or left arm) and time of study vaccine administration to the subject will be recorded on the appropriate DCF. Subjects will be observed in the clinic for at least 20 minutes after the second study vaccination.

The second study vaccination site will be examined, post-administration reactogenicity assessments will be performed, and any AE/SAEs will be recorded on the appropriate DCF prior to discharge from the clinic.

- Subjects will be provided with a Memory Aid and other study-related materials to record daily oral temperature, solicited injection site and systemic reactions, unsolicited AEs, and concomitant medications. Subjects will be encouraged to take their oral temperature around the same time each day. Subjects must not eat or drink anything hot or cold, or smoke within 10 minutes prior to taking oral temperature. Subjects will be instructed on how to use their Memory Aid and how to measure and record AEs prior to discharge from the clinic. Subjects will be instructed to notify the study center if they develop any severe reactions after the second study vaccination. If the site PI or appropriate sub-investigator deems the reaction severe enough, further instructions will be given to the subject on the proper course of action, including a return to the clinic for immediate evaluation if appropriate.

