3.2.2 Secondary

Safety:

- Occurrence of all unsolicited non-serious AEs from the time of each study vaccination through approximately 21 days after each study vaccination.
- Occurrence of all MAAEs, including NOCMCs and PIMMCs, from the time of the first study vaccination through approximately 12 months after the last study vaccination.

Immunogenicity:

- For HAI and Neut antibodies, percentage of subjects achieving seroconversion against the influenza A/H7N9 study vaccine viruses approximately 21 days after the first study vaccination as well as immediately prior to and approximately 180 days after the second study vaccination.
- For HAI and Neut antibodies, percentage of subjects achieving titer \geq 1:40 against the influenza A/H7N9 study vaccine viruses immediately prior to each study vaccination, approximately 21 days after the first study vaccination and approximately 180 days after the second study vaccination.

- GMTs of serum HAI and Neut antibodies against the influenza A/H7N9 study vaccine viruses immediately prior to each study vaccination, approximately 21 days after the first study vaccination and approximately 180 days after the second study vaccination.

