8.4 Early Termination Visit (if needed)

The following activities will be performed at the Early Termination Visit on subjects who withdraw, or are withdrawn or terminated from this trial:

- Interim medical history, including an assessment for new medical conditions, stability of chronic diseases and symptoms suggestive of PIMMCs, will be obtained by interview of subjects and any changes since the previous clinic visit or phone call will be noted.
- All concomitant medications will be recorded on the appropriate DCF (if prior to 21 days after the last study vaccination). Receipt of any non-study influenza vaccines will also be recorded on the appropriate DCF (if within 180 days after the last study vaccination).
- All AE/SAEs will be recorded on the appropriate DCF. AEs limited to SAEs and MAAEs, including NOCMCs and PIMMCs, that have occurred since the previous clinic visit or phone call will be solicited (if after 21 days after the last study vaccination).
- Memory Aid information will be reviewed with subjects (if within 7 days after the last study vaccination).

- Vital signs, including oral temperature, pulse and BP, may be obtained if indicated. Subjects must not eat or drink anything hot or cold, or smoke within 10 minutes prior to taking oral temperature.
- A targeted physical examination, including an assessment for signs suggestive of PIMMCs, may be performed, if indicated based on review of interim medical history, by a study clinician licensed to make medical diagnoses and listed on the Form FDA 1572 as the site PI or sub-investigator.
- The study vaccination site will be examined (if within 7 days after the last study vaccination).
- Post-administration reactogenicity assessments will be performed (if within 7 days after the last study vaccination).
- Approximately 10 mL of venous blood will be collected for clinical safety labs (WBC, Hgb, PLT, ALT, T. Bili, Cr) to be performed by the central (clinical) laboratory (if within 7 days after the last study vaccination).
- Approximately 15 mL of venous blood will be collected for serological assays (if within 21 days after the last study vaccination).
- Approximately 24 mL of venous blood will be collected for cellular immunology assays (if within 21 days after the last study vaccination).
- Approximately 16 mL of venous blood will be collected for future research (if within 21 days after the last study vaccination).

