9.3 Reporting Procedures

Solicited injection site and systemic reactogenicity events will be documented and reported from the time of each study vaccination through 7 days after each study vaccination.

Clinical safety laboratory AEs will be documented and reported from the time of each study vaccination through approximately 7 days after each study vaccination.

Unsolicited non-serious AEs will be documented and reported from the time of each study vaccination through approximately 21 days after each study vaccination.

SAEs and MAAEs, including NOCMCs and PIMMCs, will be documented and reported from the time of the first study vaccination through approximately 12 months after the last study vaccination.

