9.4 Type and Duration of Follow-up of Subjects after Adverse Events

AEs will be collected, assessed and followed through resolution from the time of each study vaccination through approximately 21 days after each study vaccination.

SAEs and MAAEs, including NOCMCs and PIMMCs, will be collected, assessed and followed from the time of the first study vaccination through resolution even if this extends beyond the trial-reporting period (approximately 12 months after the last study vaccination).

Resolution of an AE/SAE is defined as the return to pretreatment status or stabilization of the condition with the expectation that it will remain chronic.

Follow-up procedures, evaluations and outcomes will be recorded on the appropriate DCF and entered into the eCRF.

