- & Inclusive of reactogenicity assessments performed on the day of each study vaccination through 7 days after each study vaccination.
- 4 AEs limited to SAEs and MAAEs, including NOCMCs and PIMMCs, for subjects who are discontinued from receipt of the second study vaccination and being followed for safety.

Table 16: Follow-Up Period for Treatment Arms 1 and 4 (Including Early Termination and Unscheduled Visits)

Study Visit Number	V12**	V13	V14**	V15	V16**	Early Termination (if needed)	Unscheduled (if needed)
Study Day post first study vaccination	D82	D112	D142	D202	D387		
Study Day post second study vaccination	D61±7d	D91±14d	D121±14d	D181±14d	D366±14d		
Study Procedure/Evaluation							
Medical History [@]		X		X		X	X (if indicated)
Concomitant Medications ^c	X	X	X	X		X (if prior to 21 days after last study vaccination and receipt of any non-study influenza vaccines if within 180 days after last study vaccination)	X (if prior to 21 days after last study vaccination and receipt of any non-study influenza vaccines if within 180 days after last study vaccination)
Vital Signs (Oral Temperature [%] , Pulse and BP)						X (may be obtained if indicated)	X (may be obtained if indicated)
Physical Examination		{X}		{X}		{X}	{X}
Venous Blood Collection for Clinical Safety Laboratory Evaluations~						X (if within 7 days after last study vaccination)	X (if indicated)
Venous Blood Collection for Serological Assays				X ^ψ		X (if within 21 days after last study vaccination)	X (if within 21 days after last study vaccination)
Venous Blood Collection for Cellular Immunology Assays		X		X		X (if within 21 days after last study vaccination)	X (if within 21 days after last study vaccination)
Venous Blood Collection for Future Research		X		X		X (if within 21 days after last study vaccination)	X (if within 21 days after last study vaccination)
Examine Study Vaccination Site						X (if within 7 days after last study vaccination)	X (if within 7 days after last study vaccination)

Study Visit Number	V12**	V13	V14**	V15	V16**	Early Termination (if needed)	Unscheduled (if needed)
Study Day post first study vaccination	D82	D112	D142	D202	D387		
Study Day post second study vaccination	D61±7d	D91±14d	D121±14d	D181±14d	D366±14d		
Study Procedure/Evaluation							
Post-Administration Reactogenicity Assessments						X (if within 7 days after last study vaccination)	X (if within 7 days after last study vaccination)

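### In Arms 1 and 4, Visit 06 closes the dose 1 unsolicited-AE window, but subjects already stopped from dose 2 have only SAEs and MAAEs recorded there, against the protocol's own 21-day rule

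*Protocol*

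**What the plan says.** **General rule.** The secondary safety outcome (Protocol 3.2.2) is "Occurrence of all unsolicited non-serious AEs from the time of each study vaccination through approximately 21 days after each study vaccination". Section 9.1 lists the same period. Section 9.3 states "Unsolicited non-serious AEs will be documented and reported from the time of each study vaccination through approximately 21 days after each study vaccination", and Section 9.4 states "AEs will be collected, assessed and followed through resolution from the time of each study vaccination through approximately 21 days after each study vaccination". None of these makes an exception for a subject who will not receive dose 2.

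**Visit rule, Arms 1 and 4.** Section 8.2.7 covers "Visit 06, Day 22 (Window: Day 22+7 days post first study vaccination), Treatment Arms 1 and 4", together with Visit 08 (Day 121) for the other arms. Its AE item first asks for all AE/SAEs before vaccination. It then adds "Note: AEs will be limited to SAEs and MAAEs, including NOCMCs and" PIMMCs for subjects discontinued from dose 2 and followed for safety. Footnote 4 in Appendix A, marked on V06 in Table 15, says the same: "AEs limited to SAEs and MAAEs, including NOCMCs and PIMMCs, for subjects who are discontinued from receipt of the second study vaccination". SAP Table 2 carries this footnote on V06 too.

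**Visit rule elsewhere.** At Day 22 in Arms 2, 3, 5 and 6 (Section 8.2.5) the instruction is simply "All AE/SAEs will be recorded on the appropriate DCF", and V06 in Table 17 has no footnote 4. Sections 8.4 and 8.5 tie the SAE/MAAE limit to elapsed time. They apply it to events "that have occurred since the previous clinic visit or phone call will be solicited (if after 21 days after the last study vaccination").

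**The concern.** One visit carries two incompatible instructions. Under Sections 3.2.2, 9.1, 9.3 and 9.4, an Arm 1 or 4 subject who had dose 1 and was then stopped should have every unsolicited AE recorded up to about Day 22. Under Section 8.2.7 and footnote 4, the visit at which those last days would be collected records only SAEs and MAAEs.

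The subjects concerned are not a random subset. One route to being stopped before Visit 06 is a Grade 3 AE without alternative etiology in the 8 days after dose 1 (Section 5.2.3), so some are selected for dose 1 toxicity. The gap also arises only in the 21-day arms, although Arms 1-3 share one first dose and Arms 4-6 share another. SAP Section 9.3.2 uses the whole Safety population as denominator, so days on which nothing was asked would count as event-free.

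**Working it through.** **Inputs**
- Dose 1 window: 21 days after vaccination (Protocol 3.2.2, 9.3, 9.4).
- Visit 05: Day 15±1, all AE/SAEs recorded (8.2.4). This is the last unrestricted scheduled recording before Visit 06. The Memory Aid covers only 7 days after vaccination (7.1).
- Visit 06, Arms 1 and 4: Day 22+7 (8.2.7).
- Planning rate: 5% of subjects in the 21-day arms excluded from the per-protocol analysis (11.4.2).
- Arms 1 and 4: 30 + 30 = 60 subjects (Table 1).

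**Reproducing the plan's figure.** Vaccination is on Day 1, so days after vaccination = Day - 1. Visit 06 on Day 22 to Day 29 is 21 to 28 days after dose 1, which matches SAP Section 4.4.5. The same rule gives 113 to 134 days for Day 121-7/+14, which also matches.

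**Share of the window after the last full recording** = (21 - days after dose 1 at Visit 05) / 21

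| Visit 05 on | Days after dose 1 | Uncovered | Share of 21 days | Share of the SAP's Day 9-22 column (14 days) |
|---|---|---|---|---|
| Day 14 | 13 | 8 | 38% | 57% |
| Day 15 | 14 | 7 | 33% | 50% |
| Day 16 | 15 | 6 | 29% | 43% |

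The SAP's implementation notes extend its Day 22 events to the actual 21-day visit. If Visit 06 falls on Day 29, the uncovered part is (28 - 14)/28 = 50%. Over the Visit 05 window the range is 13/28 = 46% to 15/28 = 54%.

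**Subjects affected (assumption).** 5% × 60 = 3. This is a ceiling. The 5% also covers loss to follow-up and protocol deviations, and a lost subject is not affected by the note.

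**Effect on a table.** One subject in an arm of 30 whose only unsolicited event is missed changes that arm's incidence by 1/30 = 3.3 percentage points.

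**Is Section 8.4 wording a cure?** Its condition is the date of the visit, not the onset of the event. If Visit 06 falls 22 to 28 days after dose 1, the visit is past 21 days. Non-serious events since Visit 05 would then still be dropped, including those with onset inside the window.

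**The case against.** The strongest reply is that loss of data is not established. Sections 9.3 and 9.4 still require full collection, and Section 9.2.5 makes the investigator responsible for recording all observed or reported events. Section 5.2.4 refers to a Manual of Procedures, not available here, for follow-up of one-dose subjects. Some sites may therefore record everything. This stands as a limit on certainty, but it also means that capture could vary by site.

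The size is also small. SAEs and MAAEs, including NOCMCs and PIMMCs, are still recorded. Subjects may be stopped for refusal or noncompliance, so selection is only partly by toxicity. Unsolicited AEs are summarized descriptively, with no planned between-arm test. A reader might infer that the arm comparison is materially biased. With so few subjects, the documents support only a possible under-count in Arms 1 and 4.

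Two further readings are tempting but not supported:
- **A trial halt would put all 60 subjects of Arms 1 and 4 under the note.** Section 9.5 pauses enrollment and vaccination pending DSMB review, and a paused subject is not discontinued from dose 2. Nor would 60 be waiting at once. With even accrual (an assumption) over the planned 12 weeks, 60/12 = 5 subjects enter these arms per week. At 3 to 4 weeks between doses, about 15 to 20 are unboosted at any time.
- **A subject barred by a Grade 2 event still ongoing at Day 22 loses the same data.** That subject arrives not yet discontinued. Section 8.2.7 records all AE/SAEs before vaccination, and the Section 5.2.3 checks need that information. The text is at best ambiguous here, so the point rests on subjects stopped before Visit 06.

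**Conclusion.** The contradiction is real and should be corrected. For Arm 1 and 4 subjects already discontinued from dose 2 when they reach Visit 06, the visit-level instruction as written leaves about one third of the dose 1 window (7 of 21 days) without recording of non-serious, non-medically-attended events. SAP Tables 99 and 101-103 would still count these subjects as fully observed, and the event counts in Tables 104 and 105 would omit the missing events.

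The conclusion assumes that sites follow the note rather than Sections 9.3 and 9.4, and that the 5% planning rate bounds the number stopped. At about 3 subjects or fewer, the effect on the trial's safety conclusions is small. The case for acting is that the affected subjects are partly selected for dose 1 toxicity, that no reason is given for treating the 21-day arms differently, and that the correction costs almost nothing.

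**What to change.** Reconcile the passages as follows:
- Remove footnote 4 from V06 in Protocol Table 15 and SAP Table 2.
- Confine the Section 8.2.7 note to Visit 08 (Arms 2, 3, 5 and 6), where the dose 1 window has long closed. The SAE/MAAE-only limit in Arms 1 and 4 then starts after V06. Table 17 does not mark footnote 4 on V08; this mismatch is harmless and can be tidied in the same edit.
- If a time-based wording is preferred, key it to event onset more than 21 days after the last study vaccination, not to visit date as in Section 8.4.

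With either route, none of the 21 days is left unrecorded. The cost is a short edit to the protocol, the two schedules and, where needed, the Manual of Procedures, plus a few more non-serious AEs to record. No visit, blood draw or dosing rule changes. Section 14.3 indicates that enrollment is complete. If Visit 06 has already passed, the clinical study report should state how many Arm 1 and 4 subjects were stopped before it, and how their AEs after Visit 05 were recorded.
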